Based on the literature review, CRF is a significant and distressing problem for leukemia patients. Due to the disease itself, considerations for hemoglobin, platelets, and patient activity safety severely limit the available intervention options for fatigue. Music therapy is a non-invasive, safe, comfortable, and easily administered nursing intervention. Following appropriate assessment and selection of resonant music based on client preferences, it can be implemented by healthcare providers or by the patients' families.

Discrepancies exist between domestic (Taiwanese) and international music therapy practices, primarily in education systems, professional certification, legal regulations, and cultural factors. Currently, Taiwan lacks a formal certification system for music

therapists, unlike many other countries. Compounded by financial constraints that often preclude hiring therapists with foreign qualifications, the implementation of standardized MT is challenging.

Therefore, this study aims to recruit patients newly diagnosed with leukemia who are undergoing conventional chemotherapy. It will utilize music therapy as an intervention to investigate its effects on fatigue and clinical laboratory values.

Research Methods

This chapter is divided into nine sections, detailing the methods and procedures of this study. It includes: (1) research framework, (2) research design, (3) research setting and participants, (4) sample size, (5) the music therapy protocol, (6) research instruments and reliability/validity, (7) research procedures, (8) ethical considerations, and (9) data processing and analysis.

Research Framework

Based on the aforementioned literature review, the research framework for this study was developed as illustrated in Figure 3-1.

The primary purpose of this study is to investigate the effects of music therapy on fatigue and clinical laboratory values (e.g., White Blood Cell [WBC] count, Hemoglobin [Hb], Albumin) in patients with acute leukemia undergoing chemotherapy. The study is designed to provide music therapy to this patient population, utilizing fatigue severity and clinical laboratory values as the primary outcome variables. This framework will be used to compare the differences in these key outcome variables between the music therapy group and the standard care group.

Research Design

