This study employs an **experimental research design** utilizing **randomized assignment** and **repeated measures**. Participants who consent to the study will be allocated to either the experimental group (Group A) or the control group (Group B). Group A participants will listen to self-selected music in addition to receiving standard care. Group B participants will receive standard care only. The objective is to evaluate the effectiveness of music therapy in alleviating fatigue. A total of 44 patients with leukemia undergoing their initial chemotherapy will be recruited, with 22 participants allocated to each group.

The measurement process will be conducted in two parts:

1. **Primary Data Collection:** Data will be collected at two main time points: upon admission for initial chemotherapy (Baseline, T0) and on Day 21 of the

chemotherapy cycle (T1). On Day 21, the researcher will visit the ward to collect the required data, including the Tang's Fatigue Scale, the Fatigue Numerical Rating Scale (NRS), and clinical laboratory data. If a participant has been discharged, data will be collected via telephone interview or an online questionnaire.

2. **Symptom Diary:** Participants will record their fatigue levels using the Fatigue NRS immediately following each music therapy session.

Baseline demographic data will be collected only at T0. The measurement time points and the application of corresponding instruments are detailed in Table 3-2.

Table 1: Schedule of Research Measurements

Time	Before Chemo (T0)	Chemo Day 7	Chemo Day 14	Chemo Day 21 (T1)
Tang's Fatigue Scale	○			○
Numerical Rating Scale (NRS)	○	○	○	○
WBC	○			○
Hemoglobin	○			○
Albumin	○			○
Demographic Data	○			

Note: ○ = Data to be collected

Research Setting and Participants

This study will be conducted in the hematology-oncology ward of a medical center located in Northern Taiwan. Participants must meet the following inclusion criteria:

1. Clinically diagnosed with Acute Myeloid Leukemia (AML) by a specialist physician.
2. Scheduled to receive initial (first-time) chemotherapy.
3. Aged 20 years or older.
4. Able to communicate in Mandarin or Taiwanese.
5. Possess normal hearing ability.
6. No history of psychiatric illness and clear consciousness.
7. No prior participation in any fatigue management intervention study.
8. Understands the research purpose, voluntarily agrees to participate, and has signed the informed consent form.

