9. Willing to cooperate with all study procedures during the research period.

Participants will be **excluded** from the study if they meet the following criteria:

1. Severe hearing impairment.

2. Unstable vital signs or unclear consciousness.

III: Sample Size Calculation

The sample size was estimated based on the **Generalized Estimating Equations (GEE)** approach for repeated measures. The analysis will control for baseline demographic and disease characteristics as covariates (e.g., age, sex, education level, occupation, perceived economic status, marital status, religious beliefs, and metastasis). The dependent variables are fatigue, White Blood Cell (WBC) count, hemoglobin, and albumin.

The calculation was performed using G*Power software (version 3.1.9.7). Parameters were set as follows: a significance level (α) of 0.05, statistical power ($1-\beta$) of 0.80, a 95% confidence interval, and an anticipated **effect size of 0.21**. This calculation yielded a required sample size of 34 participants (as shown in Figure 3-2). To account for a potential attrition rate of 30%, the study aims to recruit a total of **44 participants** ($n=22$ for Group A, $n=22$ for Group B).

Music Therapy Protocol

1. Music Selection, Dosage, and Headphone Use

According to the literature, a music therapy duration of 15–30 minutes is effective for fatigue alleviation (Burns et al., 2008; Cassileth et al., 2003; Miladinia et al., 2021; Reimnitz et al., 2020; Sezgin & Bektas, 2022). Music selection will be based on individual preferences and cultural background (Tsai & Chou, 2015; Browning, 2000; Gerdner, 2000).

To ensure data integrity while considering the patient's length of stay, physical burden during chemotherapy, and protocol adherence, the music therapy intervention in this study will be administered **once daily for 21 consecutive days**. The **30-minute intervention** will commence at the start of the chemotherapy infusion. During the study, participants will be provided with a chemotherapy symptom tracking diary to confirm adherence to the music therapy protocol in the experimental group.

For reasons of personal hygiene, preference, and potential patient discharge, participants will be asked to use their own headphones. If a participant does not have headphones, a set will be provided by the researcher.

Research Instruments and Psychometric Properties

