Prior to study commencement, approval will be obtained from the Institutional Review Board (IRB). Following IRB approval, and after explaining the study to and receiving consent from the attending physicians and ward nursing staff, the researcher will conduct participant recruitment in the inpatient wards and outpatient clinics. Individuals who meet the inclusion criteria will be identified as potential participants. The researcher will explain the study's purpose and methodology to these individuals. After obtaining informed consent and a signed consent form, the researcher will administer the pre-test (T0) questionnaires. This packet includes the Demographic Data Sheet, the Tang Fatigue Rating Scale (TFRS), the G-8 screening tool, and the symptom diary. This self-administration process is expected to take approximately 10 minutes. If a participant is unable or unwilling to self-report (e.g., due to advanced age or fatigue), the researcher will conduct a structured interview to complete the questionnaires, which is estimated to take 30–40 minutes. Concurrently, all participants will be invited to join the study's official LINE group for communication. Following the collection of baseline questionnaires, a computer-generated randomization sequence will be implemented by personnel not directly involved in the study (i.e., someone other than the principal investigator) to allocate participants to either the experimental group (Group A) or the control group (Group B). Participants in Group A, after confirming their chemotherapy infusion line is properly connected, will begin listening to 30 minutes of self-selected music while concurrently receiving standard care. Participants in Group B will receive standard care only. A total of **60 participants** with Acute Myeloid Leukemia (AML) undergoing chemotherapy are expected to be recruited (n=30 per group). Both groups will be required to complete the symptom diary throughout the 21-day

study period (est. 1 minute per entry). Group A will complete the Fatigue Numerical Rating Scale (NRS) immediately following each music therapy session. Group B will complete the Fatigue NRS 30 minutes after the commencement of their chemotherapy infusion.

On Day 21 (T1), the researcher will collect the post-test data (TFRS, NRS, and G-8) in the ward. If a participant has been discharged, data will be collected via telephone interview or an online questionnaire.

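### The plan sets two unreconciled recruitment targets, 44 and 60, and 44 allows for 22.7% attrition, not the stated 30%

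*Combined protocol and SAP*

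**What the plan says.** Three sections of the combined protocol and SAP give a recruitment number for the same two-arm trial.

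- **Research Design:** "A total of 44 patients with leukemia undergoing their initial chemotherapy will be recruited, with 22 participants allocated to each group".
- **III: Sample Size Calculation:** G*Power, with α 0.05, power 0.80 and an effect size of 0.21, is said to return 34. The section continues: "To account for a potential attrition rate of 30%, the study aims to recruit a total of 44 participants", again 22 per group.
- **Research Procedures**, straight after the randomization step: "A total of 60 participants with Acute Myeloid Leukemia (AML) undergoing chemotherapy are expected to be recruited (n=30 per group").

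The number of measurements and the correlation behind the 34 are not written out. They may be in Figure 3-2, which is not shown in the copy reviewed.

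**The concern.** The recruitment target decides when enrolment ends, and the plan describes no interim analysis or other rule that would settle this. With two targets in force, the team could stop at 44 or continue to 60 and cite the protocol either way. The researcher also collects the Day 21 data, so an end of enrolment that was not fixed in advance invites the question whether results influenced it. A reader of the final report could not tell whether 44 enrolled patients meant a completed trial or one that was 16 short.

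The second problem lies inside the derivation of 44. The plan says that 44 absorbs 30% attrition and still leaves the 34 it requires. If it does not, the plan misses its own standard at the loss rate it names.

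**Working it through.** **Inputs.** From Sample Size Calculation: required number 34, attrition 30%, target 44. From Research Design: target 44 (22 + 22). From Research Procedures: target 60 (30 + 30).

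**1. Compare the targets.** Each total agrees with its own per-group figures, so a single mistyped digit is an unlikely explanation. The difference is 60 − 44 = 16, and 16/44 = 36.4%. The document has no amendment log or other text that explains 60. The 60 is described as recruited and is split by group, so it does not read as a number screened or approached.

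**2. Reproduce 44.** 34 × (1 + 0.30) = 44.2, which rounds to 44. The plan's figure therefore comes from multiplying by 1.30.

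**3. Test 44 against the stated allowance.** To keep n patients after a proportion d is lost, recruit n/(1 − d).

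- 34/(1 − 0.30) = 48.57, so 49 (49 × 0.70 = 34.3). With equal arms it is 50 (50 × 0.70 = 35).
- 44 × 0.70 = 30.8, about 31. The shortfall is (34 − 30.8)/34 = 9.4%.
- The loss that 44 can absorb is (44 − 34)/44 = 10/44 = 22.7%.

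These results do not depend on how 34 was obtained.

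**4. Test 60.** 60 × 0.70 = 42, above 34. The loss that 60 can absorb is (60 − 34)/60 = 43.3%. Neither 34 × 1.30 nor 34/0.70 gives 60.

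**5. What the shortfall could mean for power (assumptions, range only).** I assumed that 0.21 is Cohen's f and that the test is the repeated-measures within-between F test for two groups under sphericity. Then λ = N·m·f²/(1 − ρ), with m − 1 and (N − 2)(m − 1) degrees of freedom and α = 0.05. The metric, the test, m (measurements) and ρ (correlation) are all my assumptions.

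| Assumed m, ρ | Power at 31 | at 34 | at 42 |
|---|---|---|---|
| Settings that return 34 (m=2, ρ 0.65–0.66; m=3, ρ 0.56–0.58; m=4, ρ 0.48–0.50) | 0.76–0.78 | 0.81–0.82 | 0.89–0.90 |
| m=2, ρ=0.6 | 0.72 | 0.76 | 0.84 |
| m=3, ρ=0.5 | 0.71 | 0.75 | 0.84 |
| m=2, ρ=0.5 | 0.62 | 0.66 | 0.76 |

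In every row, going from 34 to 31 costs about 0.04. The lower rows are already below 0.80 at 34, so most of their deficit does not come from attrition. In Table 1, Tang's scale, WBC, hemoglobin and albumin are taken at two visits and only the NRS at four. The text therefore does not show which row applies, and I make no claim that 34 is wrong.

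**The case against.** No reading of the text removes the conflict between 44 and 60. The strongest objections limit what can be built on it.

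- **Allocation.** The two targets do not make the randomization list impossible. The plan says only that "a computer-generated randomization sequence will be implemented by personnel not directly involved in the study"; a 60-entry list in blocks of four would pass through 22/22 at entry 44 and reach 30/30 at entry 60. This stands: the conflict is about when to stop.
- **Attrition.** Multiplying by 1.30 is a common shortcut. GEE also uses partial data, so a patient lost after Day 7 or Day 14 still contributes NRS scores. Telephone or online follow-up and routine laboratory records may hold actual loss below 30%. This makes a count of completers a simplification, though less so for outcomes taken only at baseline and Day 21. It does not rescue the wording, because the plan itself sets 34 and claims a 30% allowance that 44 does not give.
- **Power.** The loss attributable to the attrition error is small, about 0.04 under every setting tried. This stands, and the severity does not rest on power.
- **Restating the allowance as 22.7%.** This fits the assumption to a number already chosen. That is a fair criticism, and it is why the fix also offers a wording that keeps the 30% expectation.

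**Conclusion.** The concern holds on both parts. The main one is the contradiction: 44 (22 per group) in two sections against 60 (30 per group) in a third, 16 patients apart and unexplained. That must be fixed. 44 is the likelier intention, since two sections agree on it and only it is derived, but this is inference and the correction does not depend on it.

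The secondary part is exact arithmetic on the plan's own figures. At 44 the allowance is 22.7%, and a 30% loss leaves about 31 against a required 34. No single power cost can be stated, because the inputs behind 34 are not in the text available.

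**What to change.** State one recruitment target, with its per-group split, in Research Design, Sample Size Calculation and Research Procedures.

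- **If the target is 44:** change Research Procedures to 44 (22 per group). In Sample Size Calculation, either say that 44 allows for up to 22.7% attrition (10 of 44), or keep 30% and say that about 31 would remain, below 34. The second option needs the resulting power, recomputed by the sponsor from its own Figure 3-2 inputs, with the number of measurements and the correlation written out.
- **If the target is 60:** change Research Design and Sample Size Calculation to 60 (30 per group). Correct the attrition step to 34/(1 − 0.30) = 48.6, so at least 50 with equal arms, and give the sponsor's actual reason for going above that to 60.

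The power values in this review rest on assumed inputs and should not be copied into the protocol. The cost is wording in three sections, plus one sponsor recomputation if the wording with about 31 remaining is chosen. Correcting the stated figures needs no added enrolment, whichever target is the actual one.

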Interventions such as acupressure, massage, and art or music therapy fall under the CAM category (Chen & Tang, 2020; Rau et al., 2023; Zick et al., 2021). Considering the specific characteristics of leukemia and the need for practical clinical application, music therapy presents as a non-invasive, safe, comfortable, and easily administered nursing intervention. It can be conveniently implemented by healthcare providers, patients themselves, or family members. Research indicates that music therapy can reduce depression, anxiety, and pain in cancer patients (Köhler et al., 2020; Li et al., 2020; SezgiN & Bektas, 2022). Unfortunately, the application of music therapy for managing CRF in leukemia patients remains limited. Therefore, this study aims to investigate the effects of music therapy on fatigue and clinical laboratory values (e.g.,

White Blood Cell [WBC] count, Hemoglobin [Hb], Albumin) in patients with acute leukemia, to provide a reference for clinical practice.

Section 1: Research Purpose

To investigate the effects of music therapy on fatigue and clinical laboratory values (White Blood Cell count, Hemoglobin, and Albumin) in patients with acute leukemia.

Section 2: Research Hypotheses

1. Patients with acute leukemia who receive music therapy will experience lower levels of fatigue during chemotherapy compared to those receiving standard care.
2. Patients with acute leukemia who receive music therapy will demonstrate improved clinical laboratory values (White Blood Cell count, Hemoglobin, and Albumin) during chemotherapy compared to those receiving standard care.

Literature Review

I. Leukemia and Its Classification

According to the Global Cancer Observatory (GLOBOCAN) (2020), the global incidence of leukemia was 5.4 per 100,000 population, with a mortality rate of 3.3 per 100,000 population (Sung et al., 2021). In Taiwan, statistics from the Ministry of Health and Welfare (2022) indicate that malignant neoplasms have remained the leading cause of death for the past four decades. Leukemia ranked 13th among cancer deaths, with an incidence rate of 2.9 per 100,000 and a mortality rate of 5.0 per 100,000.

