moderate positive correlation between WBC count and fatigue ($r = 0.63$, $p < 0.05$). However, other studies, including those on post-operative colorectal cancer patients and leukemia patients, reported no significant correlation between fatigue severity and WBC count ($\beta = -0.037$, $p = 0.588$; $\beta = 0.16$, $p = 0.29$, respectively) (Addisia et al., 2022; Wei & Li, 2018).

The possible reasons for these discrepant findings may relate to cancer type and stage. Different cancer types and stages necessitate different treatment dosages, leading to varying degrees of myelosuppression (Anand et al., 2023; Kuter, 2015). Furthermore, the timing of fatigue assessment is relevant. If assessed during chemotherapy, patients are likely experiencing side effects, including leukopenia. If survivors are assessed, the decrease in WBCs may be less pronounced. The week following chemotherapy is the period of peak side effects (Chen & Tang, 2020). Therefore, research designs should collect blood laboratory values concurrently with fatigue assessments during the patient's chemotherapy process to accurately monitor the fatigue problem. Study designs must reflect the clinical reality, synchronizing the collection of laboratory data and fatigue assessments to effectively capture the correlation between fatigue and WBC count.

2. Hemoglobin (Hb) According to the World Health Organization (WHO) and the American Association of Blood Banks (AABB), anemia is defined as $Hb < 12$ g/dl for females and < 13 g/dl for males (Lotterman & Sharma, 2022; Safiri et al., 2021). Anemia ($Hb < 12$ g/dl) can result from the cancer itself, treatments (chemo/radiotherapy), malnutrition, bone marrow infiltration, or hemorrhage (Madeddu et al., 2018; Wang et al., 2002). Chemotherapy side effects cause myelosuppression, inhibiting erythropoiesis (red blood cell production) (Jhamb et al., 2008; Thong et al., 2020). This leads to insufficient hemoglobin, which impairs systemic oxygen delivery and subsequently causes fatigue (Thong et al., 2020; Wang, 2008). While 0% to 67% of chemotherapy patients may develop anemia, some studies note that fatigue can occur even in non-anemic cancer patients (Gaston-Johansson et al., 1999).

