- **Miladinia et al. (2021)** randomized 104 acute leukemia patients (with pain and fatigue scores ≥ 3) into three groups: light massage (N=34), MT (N=33), and standard care (N=37). Interventions were 15 minutes, 3 times/week for 4 weeks. The MT group listened to self-selected instrumental music via headphones. Results showed significant inter-group differences in fatigue for

both the MT group (vs. standard care) (Cohen's $d = 1.95$, $p = 0.001$, large effect) and the massage group (vs. standard care) (Cohen's $d = 2.42$, $p = 0.001$, large effect). Fatigue in both intervention groups decreased progressively, with no significant difference between them ($p = 0.148$).

Conversely, two studies showed no significant benefit of music therapy on fatigue (Bates et al., 2017; Rosenow & Silverman, 2014).

- **Rosenow and Silverman (2014)** assigned 18 acute leukemia patients to an MT group (N=8) or standard care (N=10). The MT group received only one 30–45 minute session. The Brief Fatigue Inventory (BFI) showed no significant difference ($p = 0.173$).
- **Bates et al. (2017)** randomized 82 patients (multiple myeloma or lymphoma) undergoing ASCT to an MT group (N=37) or standard care (N=45). The MT group received two 30-minute sessions (chemo day 1 and day 5). The POMS, measured at baseline and day 5, showed no significant difference ($p = 0.173$). According to the literature, the peak of chemotherapy side effects often occurs one week *after* its completion (Chen & Tang, 2020). Therefore, conducting assessments on day 1 and day 5 may have occurred before patients reached their peak fatigue levels.

Synthesizing these articles, the **dosage** (frequency and duration) of the MT intervention is a critical consideration. The two studies with non-significant results (Bates et al., 2017; Rosenow & Silverman, 2014) had methodological limitations. The Rosenow et al. (2014) RCT had a small sample size (N=18) and a low intervention dosage (one session), which was likely insufficient. Furthermore, Bates et al. (2017) did not set an inclusion criterion for moderate-to-severe baseline fatigue (e.g., ≥ 4 points); thus, the enrolled patients may not have had significant fatigue issues at the outset.

Literature Summary

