1. Participant Demographic Data Sheet Data will be collected using Google Forms or paper questionnaires, as appropriate. This sheet includes demographic information such as age, sex, education level, occupation, perceived economic status, marital status, and religious beliefs, to be completed by the participant. The questionnaire also

includes items regarding the participant's prior musical training, frequency of daily music listening, motivations for listening, typical timing and methods of listening, and preferred activities during rest.

2. Leukemia-Related Treatment Data Sheet This data will be extracted from the patient's medical records by the researcher. It includes information on chemotherapy drugs and dosages, as well as laboratory values—specifically Absolute Neutrophil Count (ANC), Hemoglobin (Hb), and Albumin—from before chemotherapy (T0) and on Day 21 (T1).

3. Tang Fatigue Rating Scale (TFRS) While many reliable and valid fatigue scales exist globally, many have limitations. Considering that fatigue assessment should encompass physical, psychological, and activity dimensions, the TFRS was selected as the primary outcome measure for this study.

The TFRS contains 37 items across three subscales: Physical (15 items), Psychosocial (12 items), and Daily-Living (10 items). It uses a 10-point rating scale, where higher scores indicate greater fatigue severity. The TFRS underwent content validity testing by three PhD-level experts in fatigue theory and psychometrics. It was validated in a sample of 107 patients with chronic heart failure. The internal consistency (Cronbach's α) was 0.96 for the total scale, and 0.83 (Physical), 0.92 (Psychosocial), and 0.97 (Daily-Living) for the subscales. The TFRS demonstrated excellent validity: **convergent validity** with the Visual Analogue Scale for Fatigue (VAS-F) was 0.87, and **construct validity** with The Beck Depression Inventory-Second Edition (BDI-II) was 0.77 (Tang et al., 2010).

In the study by Tang et al. (2010), the TFRS also showed a significant positive correlation with the New York Heart Association (NYHA) functional class ($r = 0.75, p < 0.01$) and significant negative correlations with Ejection Fraction (EF) ($r = -0.46, p < 0.01$) and Hemoglobin (Hb) ($r = -0.27, p < 0.01$) (Tang et al., 2010).

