will be categorized into four measurement scales: nominal, ordinal, interval, and ratio (Kaur et al., 2018). Nominal and ordinal scale data are considered **categorical variables** (e.g., sex, education level, occupation, perceived economic status, marital status, religious beliefs, and chemotherapy drug names) and will be presented as frequencies (n) and percentages (%). Interval and ratio scale data are considered **continuous variables** (e.g., age, fatigue severity, Absolute Neutrophil Count [ANC], hemoglobin, and albumin) and will be presented using means, standard deviations (SD), and ranges (minimum and maximum) (Kaur et al., 2018).

- **b. Inferential Statistics:** This study utilizes an experimental design with longitudinal follow-up and repeated measures, analyzed on an **intention-to-treat (ITT)** basis. It will compare the differences in fatigue severity and clinical laboratory values between the music therapy and control groups. During the study, data attrition may occur due to factors such as disease progression or a participant's personal decision to withdraw, leading to unequal sample sizes at different measurement points. Therefore, this study will employ **Generalized Estimating Equations (GEE)** to analyze the relationship between the independent and dependent variables. GEE will be used to compare pre- and post-test values (fatigue severity, Absolute Neutrophil Count [ANC], hemoglobin, and albumin) between the experimental and control groups. A *p*-value of < 0.05 will be considered the standard for statistical significance (Ziegler & Vens, 2010).

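### The only planned fatigue contrast is T0 against Day 21, which can miss the peak the protocol describes; the Day 7, Day 14 and diary ratings have no stated role in a between-arm test

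*Combined protocol and SAP*

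**What the plan says.** - **Hypothesis.** Section 2 (Research Hypotheses) predicts that music therapy patients "will experience lower levels of fatigue during chemotherapy compared to those receiving standard care".
- **Primary measure.** Research Instruments, item 3: "the TFRS was selected as the primary outcome measure for this study".
- **Schedule.** Research Design, item 1: "Data will be collected at two main time points: upon admission for initial chemotherapy (Baseline, T0) and on Day 21 of the" chemotherapy cycle (T1). Table 1 marks the Tang scale at T0 and Day 21 only, and the fatigue NRS at T0 and Days 7, 14 and 21.
- **Diary.** Research Design, item 2: "Participants will record their fatigue levels using the Fatigue NRS immediately following each music therapy session". Research Procedures extends the diary to both arms for 21 days and has Group B rate 30 minutes after the infusion starts.
- **Post-test.** Research Procedures: "On Day 21 (T1), the researcher will collect the post-test data (TFRS, NRS, and G-8) in the ward".
- **Analysis.** Data Processing and Statistical Analysis, 2b: "GEE will be used to compare pre- and post-test values". The values listed are fatigue severity, ANC, hemoglobin and albumin. No scale is named for fatigue severity, and the interim and diary ratings are not mentioned.
- **Timing of the peak.** The white cell part of the literature review says: "The week following chemotherapy is the period of peak side effects". The hemoglobin part says fatigue peaks within a week after chemotherapy and asks that data collection be timed accordingly. The review of music trials faults an earlier negative trial because "conducting assessments on day 1 and day 5 may have occurred before patients reached their peak fatigue levels".

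**The concern.** The protocol sets a standard for timing and criticises another trial for missing it. It does not show that its own primary assessment meets that standard. There is one TFRS value after baseline, taken when the protocol already expects some patients to be at home, since it provides for telephone or online collection.

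The hypothesis is about the course of treatment, but the written test looks at one day at the end of the cycle. If the arms differ around the peak and have come together by Day 21, the planned contrast will not show it. Ratings that could show it are scheduled, but the plan does not say how they are analysed. If they are examined later without a plan, the choice of day and contrast would be made after seeing the data.

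**Working it through.** **1. The plan's own figure.** Sample Size Calculation gives effect size 0.21, alpha 0.05, power 0.80 and N = 34. It states neither the number of measurements m nor the within-patient correlation ρ. For a repeated-measures interaction with two groups, λ = f²·N·m/(1 − ρ), with df1 = m − 1 and df2 = (N − 2)(m − 1).

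- m = 4, ρ = 0.5: λ = 0.0441 × 34 × 4 / 0.5 = 12.0, df 3 and 96, power 0.823. N = 34 is reproduced.
- m = 2, ρ = 0.5: λ = 0.0441 × 34 × 2 / 0.5 = 6.0, df 1 and 32, power 0.66. N = 48 would be needed.
- m = 2, other ρ: N = 66 at ρ = 0.3, 34 at ρ = 0.65 and 30 at ρ = 0.7.

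Four measurements match the NRS schedule and two match the TFRS. Because ρ is not stated, 34 fits either design, so it does not settle which time points were meant to enter the GEE.

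**2. Where Day 21 falls.** Let administration end on Day D. The week after chemotherapy is then Days D + 1 to D + 7. The documents do not give D, so the values below are assumptions.

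| D | Stated window | Day 21 relative to window | Scheduled NRS days inside |
|---|---|---|---|
| 5 | 6–12 | 9 days after | 7 |
| 7 | 8–14 | 7 days after | 14 |
| 10 | 11–17 | 4 days after | 14 |
| 14 | 15–21 | last day | 21 |
| 21 | 22–28 | before it | none |

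Day 21 lies after the window whenever D < 14 and inside it for D from 14 to 20. Days 7, 14 and 21 are seven days apart, so a seven-day window starting by Day 21 contains exactly one of them. The scheduled NRS therefore covers the window for any D up to 20; the TFRS covers it only for D from 14 to 20.

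**3. What a smaller difference on Day 21 would cost (illustration).** A two-sided 0.05 test with 80% power has noncentrality 1.96 + 0.84 = 2.80.

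- 75% of the peak difference retained: 0.75 × 2.80 = 2.10; Φ(2.10 − 1.96) = 0.556, about 56% power.
- 50% retained: 0.50 × 2.80 = 1.40; Φ(1.40 − 1.96) = 0.288, about 29% power.

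**4. What averaging gains (illustration).** The variance of a mean of three equally correlated ratings, relative to one rating, is (1 + 2r)/3. For r = 0.3, 0.5 and 0.7 this is 0.53, 0.67 and 0.80, a reduction of 47%, 33% and 20%. It becomes a gain in power only if the arm difference is of similar size on the three days.

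**5. Comparability of the ratings.** The session lasts 30 minutes from the start of infusion, so on infusion days both arms make the diary rating at about the same clock point, but Group A has just finished listening to music. That rating mixes any lasting effect with the immediate one. On a day without infusion, Group B's rating has no anchor. The plan does not say whether the Day 7 and Day 14 entries in Table 1 are diary entries or separate ratings.

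**The case against.** A reader might infer that hypothesis 1 is tested largely after the peak. The documents do not support that. The peak is counted from the end of chemotherapy, and no section gives that day. T1 is labelled as a chemotherapy day, and the daily sessions over 21 days are tied to the start of infusion. Read literally, Day 21 could be during chemotherapy, or even before the peak.

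A reader might also infer that the interim ratings are deliberately excluded. That goes too far as well. The analysis section describes longitudinal follow-up with repeated measures and justifies GEE by unequal numbers across measurement points, and the sample size is compatible with four measurements. What can be shown is that the one stated comparison is pre-test against post-test and that no role is given to the other ratings.

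The design choice also has a rationale. Day 21 is the end of the full course of sessions, the review treats dosage as critical, and one cited trial reports fatigue falling progressively in its intervention arms, so the arm difference could grow with time. Day 21 pairs the TFRS with the laboratory values. A sparse long scale with a frequent single-item rating limits burden, which the hemoglobin part of the review favours. Nor does this trial simply repeat the criticised one, because both arms rate fatigue through Day 21.

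All of this stands. It supports keeping the TFRS on Day 21 as primary, particularly as the section defining fatigue calls for multidimensional tools. It does not supply an analysis of fatigue between T0 and Day 21.

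**Conclusion.** The point holds in a limited form. The primary scale has no assessment between T0 and Day 21, the stated comparison is pre/post, and the scheduled Day 7 and Day 14 NRS ratings and the diary have no stated role in a between-arm test. The Day 21 contrast can miss the peak that the protocol itself describes, and does so if administration ends before Day 14. A null result on that day would not show absence of an effect during chemotherapy.

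That Day 21 is after the peak is not established, because it depends on an end day the documents omit. The 56% and 29% power figures rest on assumed retention of the effect, and the 20% to 47% variance reductions on assumed correlations; none is an estimate for this trial. This is a worthwhile, inexpensive improvement, and it does not invalidate the primary outcome.

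**What to change.** In Data Processing and Statistical Analysis, 2b:

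- Name the TFRS on Day 21 as the primary fatigue outcome and describe it as end-of-cycle fatigue.
- Add a pre-specified GEE of the fatigue NRS at T0 and Days 7, 14 and 21, with arm, day and their interaction. Make the arm difference averaged over Days 7, 14 and 21 the main NRS contrast, ranked below the TFRS, and report the difference on each day.
- State whether the remaining diary ratings are descriptive or analysed.

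In Research Design and Research Procedures, have the scheduled NRS ratings taken before that day's music session and at the same time of day in both arms, and say that they are separate from the diary entry made after the session.

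Cost: wording in the analysis section, a rating-time instruction, and a separate one-item rating on the scheduled days where the diary entry would otherwise have served. The downside is one more fatigue contrast to rank, on a single-item scale that is less rich than the TFRS. No additional visit or blood draw is needed.
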